6.3 Method for Assigning Subjects to Product Sequences

On Day -1, the subjects will be randomized to one of the six sequences of the 3-period cross-over design (section 4.1) by means of a permuted-block schema. Details about the randomization process will be included in the Data Management Plan (DMP).

The following quotas will be applied on the total number of randomized subjects:

- At least 40% of each sex will be represented
- At least 15% of Black, Asian, American Indian or Alaska native, Native Hawaiian, and other Pacific Islander race will be represented

If a sufficient number of subjects are already randomized to the study sequences, any additional subjects (alternates) will be discontinued from the study prior to randomization and will enter the 3-day Safety Follow-Up Period (section 5.2).

Block size and other randomization details will be available in the randomization plan. The randomization scheme will be generated by an independent statistician and neither the Sponsor staff, nor Investigator or study subjects will have access to the randomization scheme during study conduct.

6.4 Blinding

This is an open-label study. Therefore, the subjects, the Investigator, the PMP and CRO personnel will be unblinded to the subject's sequence and product use.

6.5 Investigational Product Accountability and Compliance

6.5.1 Dispensing Investigational Product

From Day -1 until Day 3, P4M3 Gen 2.0, comprising of a fully charged Battery unit with a full Cartridge, and cigarettes will be dispensed by the investigational site staff, as per the study design. For each product use, subjects will receive a full Cartridge.

Each dispensing of investigational products to the subject will be recorded in a log.

6.5.2 Storage and Accountability

P4M3 Gen 2.0 components and cigarettes will be stored in a secured storage place at the investigational site with access limited to the authorized personnel only. The distribution and return of investigational products will be controlled by qualified and appropriately trained investigational site staff. Subjects will return P4M3 Gen 2.0, comprising of the P4M3 Gen 2.0 Battery unit and the P4M3 Gen 2.0 Cartridge, immediately after the 6 minutes *ad libitum* use

Confidentiality Statement

Data and information contained in this document are considered to constitute trade secrets and confidential commercial information, and the legal protections provided to such trade secrets and confidential information are hereby claimed under the provisions of applicable law. No part of this document may be publicly disclosed without the written consent of Philip Morris Products S.A.

to the investigational site staff for accountability and P4M3 Gen 2.0 Cartridge weighing (section 7.8.3).

Smoked cigarettes will be documented and cigarette butts will be collected by investigational site staff.

6.5.3 Investigational Product Retention

Used and unused P4M3 Gen 2.0 Battery units and P4M3 Gen 2.0 Cartridges will be destroyed or returned to the Sponsor upon study completion. Smoked cigarette butts will be destroyed upon study completion.

6.5.4 Compliance to Investigational Products

Compliance will be ensured by strict distribution and collection of any used and unused P4M3 Gen 2.0, comprising of the P4M3 Gen 2.0 Battery unit and the P4M3 Gen 2.0 Cartridge, and cigarettes / cigarette butts by designated investigational site staff.

6.6 Restrictions

6.6.1 Smoking Restrictions

During the Screening period, subjects will be allowed to use any nicotine/tobacco-containing products according to their usual habits except during the procedures of the Screening Visit (section 9.1). Spirometry assessments at Screening and at Day -1 will be performed 1 hour after stopping smoking (section 9.1 and 9.2).

From Admission (Day -1) to Discharge (Day 3) or early termination, use of any nicotine/tobacco containing products, except use as per study design of the allocated product will not be permitted.

A nicotine washout period of at least 12 hours should be respected before product use at Day 1 to Day 3.

6.6.2 Dietary Restrictions

A standard diet will be designed for the whole confinement period. For each meal, the caloric and fat content should be controlled to avoid a “high-fat” diet. The FDA guidance on food-effect studies for bioequivalence testing identifies a “high-fat” diet as a diet which contains “approximately 50 percent of total caloric content of the meal [from fat] and is high in calories (approximately 800 to 1000 calories) [20].”

Confidentiality Statement

Data and information contained in this document are considered to constitute trade secrets and confidential commercial information, and the legal protections provided to such trade secrets and confidential information are hereby claimed under the provisions of applicable law. No part of this document may be publicly disclosed without the written consent of Philip Morris Products S.A.

Subjects are not allowed to bring their own food or beverages to the investigational site. Meals will be served as described in [section 9](#). Additional light snacks, fruits, and raw vegetables can be distributed to the subjects without restrictions at any time during confinement (except during product use periods) if they comply with the standard diet. Consumption of water is allowed as desired. Consumption of quinine-containing drinks (e.g., tonic water) is not allowed. Subjects should refrain from ingesting foods or beverages containing grapefruit or Seville-type (sour) oranges and marmalade from 7 days prior to Day -1 and throughout the study. The same menu and meal schedule will be administered uniformly for all subjects. Subjects should have fasted (black coffee or tea without sugar is possible) for at least 6 hours prior to safety laboratory assessments at Day -1 and on Day 3.

Subjects should refrain from strenuous and/or unaccustomed exercise throughout the entire course of the study.

6.7 Concomitant Medication

All medication taken within 4 weeks prior to the ICF signature will be considered prior medication. All medication taken from Screening Visit to end of the Safety Follow-Up Period will be considered concomitant medication.

Only progesterone-containing hormonal contraception will be allowed. Hormonal contraception containing estrogens or hormone replacement therapy will be prohibited and subjects will be excluded based on eligibility criteria.

Any medication with an impact on the CYP2A6 metabolism [\[21\]](#) (used as prescription and over-the-counter products), including, but not limited to medications listed in [Table 2](#), must be avoided as CYP2A6 is involved in the nicotine metabolism. To be eligible for the study, any medication with impact on CYP2A6 metabolism must have been discontinued at least 14 days prior to Day -1 or for at least 5 half-lives (whichever is longer). It is at the discretion of the Investigator to assess if a termination of such medication is medically justified and safe for the subject. In addition, they should not be used during the entire study until the time of Discharge or early termination. Prior to database lock, concomitant medication will be reviewed for their potential impact on CYP2A6 activity and the study results.

Confidentiality Statement

Data and information contained in this document are considered to constitute trade secrets and confidential commercial information, and the legal protections provided to such trade secrets and confidential information are hereby claimed under the provisions of applicable law. No part of this document may be publicly disclosed without the written consent of Philip Morris Products S.A.

Table 2 CYP2A6: Substrates, Inhibitors, and Inducers

Inhibitors	Drug Class
Amiodarone	Antiarrhythmic agent, Class III
Desipramine	Antidepressant
Isoniazid	Anti-bacterial drug
Ketoconazole	Anti-fungal medication
Letrozole	Anti-estrogen drug
Methoxsalen	Systemic psoralens
Miconazole	Anti-fungal medication
Tranylcypromine	Antidepressant
Inducers	Drug Class
Amobarbital	Barbiturate
Pentobarbital	Barbiturates
Phenobarbital	Barbiturates/anticonvulsants
Rifampin	Antimycobacterials
Secobarbital	Barbiturates
Substrates	Drug Class
Dexmedetomidine	α_2 -Adrenoceptor, sedative
Ifosfamide	Anti-cancer, alkylating agents

Use of over-the-counter medication will be restricted from Admission (Day -1) to Discharge or early termination, although exceptions may be made on a case-by-case basis at the discretion of the Investigator.

Use of any other concomitant medication will be evaluated on a case-by-case basis by the Investigator. Any concomitant medication used will be fully documented (section [7.4.2](#)).

Confidentiality Statement

Data and information contained in this document are considered to constitute trade secrets and confidential commercial information, and the legal protections provided to such trade secrets and confidential information are hereby claimed under the provisions of applicable law. No part of this document may be publicly disclosed without the written consent of Philip Morris Products S.A.

7 STUDY PROCEDURES

Investigational site staff performing or recording study assessments must have the appropriate and fully documented training. An overview of study assessments and time points is shown in the schedule of events ([Appendix A](#)). Appropriate medical advice will be provided to the subject in case of any medical findings requiring health care. Site personnel will adhere to the site's standard operating procedures (SOPs) for study related procedures.

7.1 Informed Consent

Subjects will be asked to provide their written consent to participate in the study (section [1.3](#)). Study assessments must only start after the time of ICF signature by the subject.

7.2 Information on the Risk of Smoking and Smoking Cessation Advice and Debriefing on P4M3 Gen 2.0

At the Screening Visit, before enrollment at Day -1 and at Discharge (Day 3), subjects will receive 1) information on the risks of smoking, 2) smoking cessation advice, and 3) debriefing on P4M3 Gen 2.0 as described in the Schedule of events ([Appendix A](#)).

The information on the risk of smoking and advice on smoking cessation will take the form of a brief interview according to the WHO recommendations [\[22\]](#). The debriefing of subjects on P4M3 Gen 2.0 will address any intended or unintended beliefs that subjects may have about P4M3 Gen 2.0. The goal of the debriefing is to help ensure that subjects enter and exit the study with an accurate understanding of the product risks.

Details of the sessions will be recorded in the source document file. This information will be given to the subjects on an individual basis during a face-to-face meeting between the subject and the Investigator or may be given in a group session.

7.3 Support during Abstinence from any Tobacco and Nicotine Containing Products

Subjects will be offered support during periods of abstinence from any nicotine/tobacco containing products during the study from Day -1 to Discharge by the Investigator and/or investigational site staff as per Schedule of events. Support resources will include counselling and assistance, entertainment, monitoring of the subject's behavior, AEs, and the subject's mood, clinical tests e.g., vital signs, physical examination.

Confidentiality Statement

Data and information contained in this document are considered to constitute trade secrets and confidential commercial information, and the legal protections provided to such trade secrets and confidential information are hereby claimed under the provisions of applicable law. No part of this document may be publicly disclosed without the written consent of Philip Morris Products S.A.

7.4 Clinical Assessments

7.4.1 Demographic Data

Sex, date of birth, race and ethnicity will be recorded for each subject as described in the Schedule of events.

7.4.2 Medical History, Concomitant Disease, Prior and Concomitant Medication

Relevant medical history or any concomitant disease will be documented at the Screening Visit. Medical history is defined as any condition that started and ended prior to the ICF signature at the Screening Visit. A concomitant disease is defined as any condition that is either detected or is still ongoing at the time of ICF signature. The final status of any concomitant disease (i.e., stop date or ongoing) should be verified at each visit.

Prior medication taken within 4 weeks prior to the Screening Visit and any concomitant medication will be documented. Any medication started prior to the Screening Visit and still being taken by the subject will be considered concomitant medication. Medication initiated after the Screening Visit will also be referred to as concomitant medication. The definition of concomitant medication applies to both prescribed and over-the-counter products.

Records of medication taken should include the drug name (preferably both generic and trade name), route of administration (e.g., oral, intravenous), dose and frequency (expressed in metric units, for example, mg, mL, or IU), indication, and the start and, if applicable, the stop date (day, month, and year). Therapy changes (including changes of regimen) during the study have to be documented. If a concomitant medication is still being taken by the subject at the end of the study, this will be recorded in the CRF.

7.4.3 Physical Examination

Physical examinations will be conducted as described in the Schedule of events.

A physical examination will include review of general appearance, hair and skin, head, eyes, ears, nose and throat, neck, thyroid gland, chest, lungs, back, abdomen, dentition, gastrointestinal, cardiovascular, musculoskeletal, and neurological systems. The physical examination is to be conducted by the Investigator or designated fully trained representative.

For those results outside of the normal range, the Investigator will determine appropriate follow-up including reporting of any AEs.

Confidentiality Statement

Data and information contained in this document are considered to constitute trade secrets and confidential commercial information, and the legal protections provided to such trade secrets and confidential information are hereby claimed under the provisions of applicable law. No part of this document may be publicly disclosed without the written consent of Philip Morris Products S.A.

7.4.4 Body Height and Weight and BMI

Body height and weight will be recorded at the Screening Visit and body-mass-index (BMI) will be calculated using the following formula:

$$\text{BMI} = \frac{\text{weight in kilograms}}{\text{height in meters}^2} = \frac{kg}{m^2}$$

The BMI will be used to assess eligibility for enrollment.

7.4.5 Vital Signs

Vital signs (systolic and diastolic blood pressure, respiratory rate and pulse rate) will be measured as described in the Schedule of events. On Day 1 to Day 3, vital signs will be assessed prior to T₀.

All parameters will be recorded in supine position after the subject has rested for at least 5 minutes. Subjects should have abstained from using any nicotine/tobacco containing products for at least 15 minutes prior to Vital signs assessment.

The Investigator will define Vital sign ranges to determine normal or abnormal results. For those results outside of the normal range, the Investigator will determine appropriate follow-up including reporting of any AEs.

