2.1.2 Description of the Product and Scientific Findings

P4M3 Gen 2.0 is an Electronic Nicotine Delivery System (ENDS) that produces an aerosol through vaporization of an e-liquid. The e-liquid is composed of propylene glycol (PG), vegetable glycerol (VG), water, nicotine, lactic acid, benzoic acid and flavors. P4M3 Gen 2.0 is a closed e-cigarette composed of a Battery unit containing all the electronics with a rechargeable battery and a disposable, replaceable Cartridge containing the e-liquid and the heating element. The P4M3 Gen 2.0 Cartridge is not refillable.

The aerosol production (heating cycle) is triggered by a pressure sensor in the Battery unit when a puff is detected. The e-liquid aerosol is produced by a heater of a fine mesh of stainless-steel wires heated by an electric current.

The aerosol generated by P4M3 Gen 2.0 is free from the majority of HPHCs associated with heating or burning tobacco, except nicotine. P4M3 Gen 2.0 does not contain tobacco and there is no combustion during use.

The non-clinical assessment is described in the Investigator's Brochure and supports the clinical assessment of P4M3 Gen 2.0 [5]. P4M3 Gen 2.0 has not been tested in humans before.

In 2016, FDA finalized a rule extending its Center for Tobacco products' (CTP's) regulatory authority to cover all tobacco products, including ENDS that meet the definition of a tobacco product. FDA regulates the manufacture, import, packaging, labeling, advertising, promotion, sale, and distribution of ENDS, including components and parts of ENDS.

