2.3.3 Anticipated Foreseeable Risks due to Investigational Product

By product design, the aerosol generated by P4M3 Gen 2.0 is free from the majority of HPHCs associated with heating or burning tobacco, except nicotine. However, given the current state of knowledge about the product, it has not yet been demonstrated that P4M3 Gen 2.0 or other e-cigarettes reduce the risk of developing smoking-related diseases compared to cigarettes.

Confidentiality Statement

Data and information contained in this document are considered to constitute trade secrets and confidential commercial information, and the legal protections provided to such trade secrets and confidential information are hereby claimed under the provisions of applicable law. No part of this document may be publicly disclosed without the written consent of Philip Morris Products S.A.

Due to sensorial and technological differences between P4M3 Gen 2.0 and cigarettes, it is possible that subjects will adapt their behavior, e.g., by modifying the number, the volume and/or duration of puffs, as well as the intensity of inhalation.

The confinement setting may also have an influence on puffing behavior and nicotine uptake.

An adult smoker using P4M3 Gen 2.0 may experience:

- Transient nicotine withdrawal symptoms (e.g., urge to smoke, irritability, anxiety feelings, restlessness, and difficulty to concentrate) similar to cravings observed during smoking cessation
- Transient symptoms suggesting mild nicotine overdose such as stimulatory effects on sympathetic tone (increased blood pressure, increased heart rate), central nervous system (tremor, blunting of emotions, and decreased ability to concentrate), gastric acid secretion, and vomiting. Individuals who experience adverse events (AEs) (suggesting excessive stimulant effects) should be instructed to reduce their intensity of product use by decreasing the number of puffs and/or the intensity of puffing
- Change in smoking habits due to study requirements and related concomitant symptoms, e.g., craving

Support during periods of abstinence from any tobacco and nicotine containing products will be provided.

Further risk mitigation will include:

- Using commonly accepted research and scientific standards (e.g., blood samples not to exceed blood donation standards)
- Medical supervision of all study subjects with follow-up of those who have experienced AEs/serious adverse events (SAEs)

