3.2 Secondary Objectives and Endpoints

The secondary objectives of this study are:

1. To describe pharmacodynamic (PD) effects (subjective effects and related behavioral assessments) of 2 variants of P4M3 Gen 2.0 and cigarettes from 6 minutes *ad libitum* use.

Endpoints (Day 1 to Day 3)

- Scores from cigarette craving by the visual analog scale (VAS)-craving assessment
- Score from product evaluation by ABOUT-Product experience questionnaire
- Score from product liking by the VAS-liking assessment

2. To describe human puffing topography (HPT) of 2 variants of P4M3 Gen 2.0 and cigarettes from the 6 minutes *ad libitum* use.

Related Endpoints (Day 1 to Day 3):

- Per-puff parameters and per-product use experience parameters from the flight recorder (FR) puffing topography device for 2 variants of P4M3 Gen 2.0 ([Appendix D](#))

3. To describe the extent of product use from 2 variants of P4M3 Gen 2.0 from the 6 minutes *ad libitum* use.

Confidentiality Statement

Data and information contained in this document are considered to constitute trade secrets and confidential commercial information, and the legal protections provided to such trade secrets and confidential information are hereby claimed under the provisions of applicable law. No part of this document may be publicly disclosed without the written consent of Philip Morris Products S.A.

Related Endpoint (Day 1 to Day 3)

- Amount of nicotine delivered derived from the weighing of P4M3 Gen 2.0 Cartridge before and after use
- 4. To evaluate the safety and tolerability during the study

Related Endpoints (from Enrollment to EOS):

- Incidence of adverse events (AEs) and serious adverse events (SAEs)
- Incidence of P4M3 Gen 2.0 product events including malfunction/misuse
- Changes in physical examination from baseline
- Changes in electrocardiogram (ECG) from baseline (Heart rate, PR, QRS, QT, QTcF interval)
- Changes in vital signs from baseline (systolic and diastolic blood pressure, pulse rate and respiratory rate)
- Concomitant medication
- Changes in standard spirometry from baseline (FEV₁, FEV₁ % predicted, FVC, FVC % predicted, FEV₁/FVC)
- Changes from baseline in clinical chemistry, hematology, and urine analysis safety panel (described in [Table 3](#))

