During/after 6 min ad libitum product use	✓	Blood sampling for nicotine PK	Post T_0 , blood will be drawn at the following time points: T1 after 1 minute + 30 seconds T2 after 2 minutes + 1 minute T3 after 4 minutes + 1 minute T4 after 6 minutes + 1 minute T5 after 8 minutes + 1 minute T6 after 10 minutes + 1 minute T7 after 12 minutes + 1 minute T8 after 15 minutes \pm 2 minutes T9 after 30 minutes \pm 2 minutes T10 after 1 hour \pm 5 minutes T11 after 2 hours \pm 5 minutes T12 after 4 hours \pm 5 minutes T13 after 10 hours \pm 5 minutes
		VAS craving assessment, VAS liking assessment	Post T_0 , assessments will be done at the following timepoints: T1 after 4 minutes \pm 1 minute T2 after 10 minutes \pm 1 minute T3 after 15 minutes \pm 1 minute T4 after 30 minutes \pm 2 minutes T5 after 1 hour \pm 5 minutes T6 after 2 hours \pm 5 minutes T7 after 4 hours \pm 5 minutes T8 after 10 hours \pm 5 minutes
Within 120 minutes after T_0		Breakfast	
Between 60 minutes and 120 minutes after T_0		ABOUT-Product experience questionnaire	
Within 120 min after T_0		Collection and weighing of used P4M3 Gen 2.0 CA35 and CM35 Cartridges, collection of cigarette buttes	

Confidentiality Statement

Data and information contained in this document are considered to constitute trade secrets and confidential commercial information, and the legal protections provided to such trade secrets and confidential information are hereby claimed under the provisions of applicable law. No part of this document may be publicly disclosed without the written consent of Philip Morris Products S.A.

Time	Blood Sample	Procedures	Additional Information
Ongoing		Support during periods of abstinence from any tobacco and nicotine containing products ✓ Clinical laboratory parameters (hematology, clinical chemistry) Urine analysis safety panel	
After at least 4 hours after T ₀		Lunch Urine pregnancy test (all female subjects) Vital signs (blood pressure, pulse rate, respiratory rate) AE/SAE, concomitant medication recording Discharge	After at least 10 hours of fasting. At least 5 min in supine position prior to measurement.

Abbreviations: AE = Adverse event; ECG = Electrocardiogram; SAE = Serious adverse event

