Data and information contained in this document are considered to constitute trade secrets and confidential commercial information, and the legal protections provided to such trade secrets and confidential information are hereby claimed under the provisions of applicable law. No part of this document may be publicly disclosed without the written consent of Philip Morris Products S.A.

- f. At Screening an ECG will be performed after signed ICF and at least 1 hour after smoking cigarettes, on Day -1 an ECG will be performed prior to enrollment, on Day 3 an ECG will be performed 60 minutes \pm 10 minutes after T₀.
- g. Blood samples should be taken in the morning of the Screening visit, Admission (Day -1) and Discharge (Day 3) or at Early termination. Subjects should have fasted for at least 10 hours prior to safety laboratory assessments except at the Screening visit and Early termination where non-fasting samples will be used.
- h. Tests for hepatitis B (HbsAg), hepatitis C (HCV antibody) virus and human immunodeficiency virus (anti-HIV1/2) will be performed at the Screening Visit.
- i. Sample taken prior to P4M3 Gen 2.0 product test.
- j. On Day -1, after enrollment, subjects will perform a product test using P4M3 Gen 2.0 Classic Auburn 3.5% variant (CA35) *ad libitum* for up to 10 minutes.
- k. On Day 1 to Day 3, subjects will smoke a single cigarette or will use one P4M3 Gen 2.0 with CA35 and CM35 variant *ad libitum* for 6 minutes (\pm 30 seconds) according to the randomized product use sequence. P4M3 Gen 2.0 use with the MDEDR puffing topography device connected with data recording for 6 minutes (\pm 30 seconds).

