10.9 Vital Signs

Vital signs (systolic and diastolic blood pressure, pulse rate, and respiratory rate) will be measured at the Screening Visit, on Admission (Day -1), Day 1 to Day 3 (Discharge) or as early termination assessments, as applicable. All parameters will be recorded in supine position after the subject has rested for at least 5 minutes. Subjects should have abstained from using any nicotine/tobacco containing products for at least 15 minutes prior to Vital signs assessment.

The Investigator will define vital sign ranges to determine normal or abnormal results. For those results outside of the normal range, the Investigator will determine appropriate follow up including reporting of any AEs.

Descriptive statistics will be reported for vital signs measurements (blood pressure, pulse, respiration, and temperature) by period. Change from baseline will be summarized in a similar manner. Baseline is defined as the result closest and prior to the first product administration, which may include unscheduled or recheck results. This will typically be the result collected on prior to T_0 on Day 1. Post product use unscheduled events or rechecks will not be included in summaries. Similarly, early termination results will not be included in summaries.

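### Every timed set of vital signs on Days 1 to 3 is taken before product use, so the planned changes from baseline cannot show an acute rise in blood pressure or pulse; the only post-use set, on Day 3, has no defined time

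*Protocol*

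**What the plan says.** Protocol 3.2 lists as a safety endpoint "Changes in vital signs from baseline (systolic and diastolic blood pressure, pulse rate and respiratory rate"). The device is new to people: Protocol 2.1.2 states "P4M3 Gen 2.0 has not been tested in humans before". Among the foreseeable transient effects, Protocol 2.3.3 names "stimulatory effects on sympathetic tone (increased blood pressure, increased heart rate").

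**Timing.** Protocol 7.4.5 reads "On Day 1 to Day 3, vital signs will be assessed prior to" T0. Appendix A note e repeats this rule, and SAP Table 3 puts Days 1, 2 and 3 before T0. Protocol Tables 8 and 9 list one pre-T0 set each for Days 1 and 2. Table 10 lists a pre-T0 set on Day 3 and then a second one in this run of entries: "Lunch Urine pregnancy test (all female subjects) Vital signs (blood pressure, pulse rate, respiratory rate) AE/SAE, concomitant medication recording Discharge". The second set carries no time relative to T0.

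**Baseline.** SAP 10.9 uses the result closest to and before the first product administration, adding "This will typically be the result collected on prior to" T0 on Day 1. Shell 15.2.3.3.1 reports changes for time points after Day 1.

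**ECG.** Heart rate is an ECG parameter, and Appendix A note f says "on Day 3 an ECG will be performed 60 minutes" (± 10 minutes) after T0.

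**The concern.** A transient nicotine effect on blood pressure or pulse is visible only if a reading is taken while nicotine is raised, and the timed vital-sign sets are placed where it is not. A table of small changes from baseline could then be taken as evidence of tolerability for a product in its first human study, although the schedule behind it could hardly have produced anything else. The one set that might help is described in one place and left out or dated differently in others. It may therefore be taken at different times after use in different subjects and reported under the wrong heading.

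**Working it through.** **Where the sets fall**

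| Source | Day 1 | Day 2 | Day 3 | Later |
|---|---|---|---|---|
| Protocol 7.4.5 and Appendix A note e | pre-T0 | pre-T0 | pre-T0 | not mentioned |
| Protocol Tables 8 to 10 | pre-T0 | pre-T0 | pre-T0, plus an untimed set listed between lunch and discharge | none |
| SAP Table 3 | pre-T0 | pre-T0 | pre-T0 | a Day 4 row with no window |

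Discharge is on Day 3, so the Day 4 row in SAP Table 3 has no matching visit. Appendix A also marks the Day 3 vital signs with note q, whose text I could not see.

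**Abstinence at each pre-T0 set.** Day 1 follows at least 12 h (Table 8). Days 2 and 3 follow about 24 h (Tables 9 and 10).

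**Nicotine remaining.** Protocol 4.2 gives an initial half-life of 1.35 h. The terminal half-life is blank in the text, but full washout is put at 3 days, or about 5 terminal half-lives, which implies 72/5 = 14.4 h. The peak is placed at 10 min, the upper end of the Tmax range in Protocol 4.2. The share f of the peak in the terminal phase is not given; I assume 5% to 20%.

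Fraction of peak at time t, with dt = t − 10 min: (1 − f) × 2^(−dt/1.35 h) + f × 2^(−dt/14.4 h)

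| Time after T0 | Fast-phase factor | Terminal-phase factor | f = 5% | f = 20% |
|---|---|---|---|---|
| 60 min (ECG) | 0.652 | 0.961 | 67% | 71% |
| 4 h (earliest lunch) | 0.140 | 0.832 | 0.95 × 0.140 + 0.05 × 0.832 = 17% | 0.80 × 0.140 + 0.20 × 0.832 = 28% |
| 10 h (last Day 3 sample) | 0.006 | 0.623 | 4% | 13% |
| 24 h (next pre-T0 set) | 0.000 | 0.318 | 2% | 6% |

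At 24 h the result is simply f × 0.318. The extreme bound, with the whole peak in the slow phase, is 32%, but that contradicts the biphasic profile described in Protocol 4.2.

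**The untimed set.** Under the opening of Protocol section 9, a procedure without a start time may be done whenever convenient that day. Taking the set's place after lunch as a guide, and the 10 h sample as a reference point near the end of the stay, the residual could be anywhere from about 28% down to 4% of peak.

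**Subjects per product.** The set follows the third-period product only. Two of the six sequences end in each product (SAP Listing 15.3.1.10), so with balanced sequences and no dropout there are 2 × 36/6 = 12 subjects per product.

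**Analysis.** Protocol 12.1.3 promises safety summaries by product. Protocol 12.6.6 and SAP 10.9 summarise vital signs by period, and shell 15.2.3.3.1 has no product column. Listing 15.3.4.4.1 shows a study product against Days 1 and 2, although those readings precede that day's use. Protocol 12.6.6 assigns Day 3 laboratory events to the previous day's product; vital signs have no such rule.

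**The case against.** Safety is a secondary, descriptive objective with no hypothesis, and acute effects are also watched through adverse events, medical supervision and the temporary stopping rule in Protocol 6.2.5. This stands as a limit on severity. Even so, an asymptomatic rise in blood pressure need not surface by those routes.

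Four stronger readings are tempting, and the documents do not support them.

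- **That every vital sign on Days 1 to 3 precedes use.** Table 10 lists a post-use set on Day 3.
- **That no set falls in the first 10 h after use.** The Table 10 set is untimed, and section 9 lets it be taken earlier. Applying only the 1.35 h half-life would also understate what remains at 10 h and 24 h.
- **That pulse goes unobserved after use.** The Day 3 ECG records heart rate at 60 ± 10 min. SAP Table 3 lists that window for Days 1, 2 and 3, while SAP 10.10 has the ECG on Day 3 only. Blood pressure is what lacks a timed post-use reading.
- **That Appendix A leaves out the discharge set.** Note q may cover it.

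A further caveat concerns baseline. If the Day -1 product test counts as the first administration, baseline moves to Day -1, where only 15 min of abstinence is required. SAP 10.9 and the shell footnote point to Day 1. Under either reading the Day 2 and Day 3 values are still abstinent ones.

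An extra use of the Day 3 reading is limited too: about 12 readings per product, compared between subjects, and at 60 min they would miss the expected peak at 7 to 10 min.

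**Conclusion.** The point holds for the timed sets. The Day 2 and Day 3 changes from the Day 1 pre-T0 value are abstinent against abstinent, with about 2% to 6% of the previous peak left, and they cannot show the acute effect foreseen in Protocol 2.3.3. That conclusion rests on document timing; the percentages rest on the implied 14.4 h half-life and the assumed 5% to 20% terminal share. One post-use set does exist on paper, but its timing is undefined and the documents disagree about it. As written, the plan yields no blood pressure reading at a known time after any randomised use. This should be corrected, but it does not affect the main pharmacokinetic objective.

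**What to change.** 1. Reconcile Protocol Table 10, 7.4.5, Appendix A notes e and q, and SAP Table 3 (including its Day 4 row) on whether and when a post-use set is taken on Day 3.
2. Give that set a defined time after T0. The existing Day 3 supine ECG slot is one option, with about 67% to 71% of peak nicotine remaining under the assumptions above. Blood sampling keeps the precedence it has in Protocol section 9. Whether a discharge check must also be kept is for the sponsor and investigator to decide.
3. In SAP 10.9 and shell 15.2.3.3.1, summarise the change in that set from the same-day pre-T0 value, by the product used that day.
4. Label the Day 2 and Day 3 pre-T0 values as following the previous day's product, and state that they are not evidence on acute effects.

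**Cost.** A small protocol amendment, signed and submitted to the review board as Protocol 1.1 requires, and added rows and labels in the SAP. If the existing set is used, no measurement is added; keeping a separate discharge check would add one. The yield is modest: about 12 subjects per product, period 3 only, compared between subjects.
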